Primary objective	The primary objective of the COPIA feasibility trial is to determine feasibility of the proposed multicentre study: 1. Determination of the likely rate of recruitment at two centres. 2. Identification of potential recruitment barriers with current protocol.
Secondary objectives	 Feasibility of maintaining follow-up rates of over 95%. Assessment of effectiveness of patient identification and screening processes. Identification and analysis of any reasons for failure to recruit patients. Assessment of trial processes, including the choice of outcome measures, and impact on staff. Assessment on completeness and feasibility of collection of the endpoints planned for the main trial.
Sample Size	50 patients across 2 centres

Summary of eligibility criteria	 Inclusion criteria Patients (male and female) aged 18 years and above Written informed consent to participate Patients undergoing Coronary Artery Bypass Graft (CABG) surgery on Cardiopulmonary bypass (CPB) with or without valve surgery Additive European System for Cardiac Operative Risk Evaluation (EuroSCORE) of 5 or higher Exclusion criteria Pregnant or lactating women Allergy to propofol Previous diagnosis or suspected malignant hyperthermia Patients with a known sensitivity to any of the IMPs or other halogenated anaesthetics Concomitant therapy with glibenclamide, allopurinol, theophylline or nicorandil (medications that may interfere with preconditioning) Inclusion in another clinical trial of an investigational medicinal product within the last 3 months.
IMP, dosage and route of administration	Volatile anaesthetics, either isoflurane, sevoflurane or desflurane, used for maintenance of anaesthesia. Administration via inhalation / ventilation through alveolar membrane in lungs. The maintenance dose of the volatile anaesthetic agent will be titrated to doses deemed necessary in order to provide sufficient depth of anaesthesia and blood pressure.
Active comparator product(s)	Propofol , an intravenous anaesthetic used for maintenance of anaesthesia. The maintenance dose of the propofol infusion will be titrated to doses deemed necessary in order to provide sufficient depth of anaesthesia without blood pressure.
Version and date of protocol	Version 1, 26 th March 2019
Proposed start date	1 st February 2019 (grant start date) 1 st September 2019 (planned recruitment start)
Proposed end date	Trial enrolment is projected to complete approximately 10 months after the start of the recruitment period. Follow-up of trial participants will complete approximately 30 days from the end of the recruitment period. The end date of the grant is the 31st January 2021.
Study duration	The duration of the trial is 24 months in total. The duration of the trial for each individual patient is 30 days .

Glossary of terms and abbreviations

ACE Angiotensinogen Converting Enzyme

AE Adverse Event
AF Atrial Fibrillation
AKI Acute Kidney Injury
AR Adverse Reaction

ARB Angiotensin Receptor Blockers

BIS Bispectral Index

CABG Coronary Artery Bypass Graft
CAM Confusion Assessment Method
CCS Canadian Cardiovascular Society

CCU Critical Care Unit

CKD Chronic Kidney Disease

COPD Chronic Obstructive Pulmonary Disease
CPAP Continuous Positive Airway Pressure

CPB Cardiopulmonary Bypass

CRF Case Report Form
CRP C-Reactive Protein
cTn Cardiac Troponin T
CTO Clinical Trials Office
CTU Clinical Trials Unit

CVA Cerebrovascular Accident
DMC Data Monitoring Committee

DSUR Development Safety Update Report

EACTA European Association of Cardiothoracic Anaesthesiology

ECG Electrocardiogram
EEG Electroencephalogram
EQ-VAS Visual Analogue Scale

EQ-5D-5L 5-level Euroqol-5D (Quality of Life Questionnaire)

GCP Good Clinical Practice

GDPR General Data Protection Regulation

HDU High Dependency Unit

HRQoL Health-related Quality of Life
hsTnT High sensitive Troponin T
IABP Intra-aortic Balloon Pump

IGFBP7 Insulin-Like Growth Factor Binding Protein 7

IHD Ischaemic Heart Disease
IME Important Medical Events

IMP Investigational Medicinal Product

KDIGO Kidney Disease Improving Global Outcomes
KHP-CTO King's Health Partners Clinical Trials Office

LSHTM London School of Hygiene and Tropical Medicine

LA Left Atrium

LCOS Low Cardiac Output Syndrome
LVEF Left ventricular Ejection Fraction

MACCE Major Adverse Cerebral or Cardiac Event

MAP Mean Arterial Pressure
MH Malignant Hyperthermia

MHRA Medicines and Healthcare Products Regulatory Agency

EudraCT Number: 2019-000171-16

MI Myocardial Infarction

mPTP Mitochondrial Permeability Transition Pore

MyC Myosin binding protein C

NGAL Neutrophil Gelatinase Associated Lipocalin

NHS National Health Service NYHA New York Heart Association

PI Principal Investigator

PIS Participant Information Sheet RCT Randomised Controlled Trial REC Research Ethics Committee

RISK Reperfusion Injury Salvage Kinases

SAE Serious Adverse Event

SAFE Survivor Activating Factor Enhancement

SAR Serious Adverse Reaction

SIRS Systematic Inflammatory Response Syndrome

SmPC Summary of Product Characteristics
SOP Standard Operating Procedure

SUSAR Suspected Unexpected Serious Adverse Reaction

TIA Transient Ischaemic Attack

TIMP-2 Tissue Inhibitor of Metalloproteinase-2

TIVA Total Intravenous Anaesthesia
TMG Trial Management Group
TNF Tumour Necrosis Factor
TSC Trial Steering Committee
UAR Unexpected Adverse Reaction

VT Ventricular Tachycardia
VF Ventricular Fibrillation

WHODAS World Health Organization Disability Assessment Schedule

2. Signature page

3.1. Need for improved cardioprotection in cardiac surgery

Coronary artery bypass graft (CABG) surgery remains the revascularisation strategy of choice for patients with multi-vessel coronary artery disease. In 2015, 16,200 isolated CABG operations and another 4100 CABG operations in combination with valve surgery were performed in the UK (http://bluebook.scts.org). The overall in-hospital mortality rate for cardiac surgery was about 2.7%, and 1-year mortality can be up to 5% [4].

The risk for patients undergoing cardiac surgery has increased recently, due to the ageing population, more patients undergoing combined CABG and valve surgery, and the presence of co-morbidities, such as diabetes, renal failure and hypertension [5]. This results in postoperative complications such as myocardial infarction (22%), acute renal injury (AKI) (38%) and stroke (2%) [4].

EudraCT Number: 2019-000171-16

Therefore, improved cardio- and organ protection during cardiac surgery can potentially result in less cardiac, renal and cerebral ischaemia in this high-risk patient group.

3.2.Inhaled anaesthesia and cardioprotection during cardiac bypass surgery

Volatile anaesthetics have been reported to protect the myocardium against myocardial injury in clinical proof-of-concept trials and meta-analyses when compared to intravenous anaesthesia, however inconclusively [2] [3] [6] [7]. The majority of these studies compared volatile anaesthetics in addition to a propofol infusion, versus propofol only. Recent studies indicate however that volatile anaesthetics administered during CPB without concomitant propofol can significantly reduce postoperative myocardial injury markers, when compared with propofol only [8] [9]. Furthermore, clinical and experimental evidence suggests that propofol has the potential to block myocardial protection [10] [11] [12] and it has been shown in patients undergoing cardiac surgery that propofol increases myocardial oxidative stress [13].

There is currently a large variation in clinical practice for cardiac procedures in the UK, given the lack of consensus regarding the benefits of volatile versus intravenous anaesthesia and lack of large trials assessing clinical outcomes, with about 50% of patients receiving intravenous anaesthesia only without volatile anaesthetics [4].

The proposed COPIA feasibility trial will compare volatile anaesthetic agents in higher risk patients undergoing cardiac surgery (including the administration of volatile anaesthetics during CPB without added propofol) with the administration of propofol only for the maintenance of anaesthesia.

Recent pharmacokinetic studies demonstrated that administering volatile anaesthetics only during CPB is feasible. It was shown that oxygenator exhaust concentrations of volatiles correlate with arterial blood concentrations [14] and that hypnosis can be maintained with adequate plasma concentrations and end-tidal concentrations of volatiles [15]. Administration of volatile anaesthetics during CPB is feasible with adequate hypnosis and amnesia and this technique has been reviewed recently [15] [16].

In summary, the proposed feasibility trial will, for the first time, compare volatile anaesthetics as the only anaesthetic agent (without propofol), with the administration of propofol only for maintenance of anaesthesia and investigate meaningful clinical outcomes. The results of the feasibility trial will be used to assess whether it is clinically acceptable and achievable to compare propofol anaesthesia with inhalational anaesthesia as the induction and maintenance agent during cardiac surgery.

3.3. Proposed multicentre randomised controlled trial

In order to perform a multicentre randomised controlled trial, with LCOS and myocardial injury as the primary outcome measures, we will assess feasibility of the rate of recruitment and protocol adherence.

EudraCT Number: 2019-000171-16

If the anticipated recruitment, follow-up and retention rates are demonstrated over a 10 month recruitment period, this would demonstrate the feasibility of a proposed 2900 patient multicentre randomised controlled trial, recruiting at 20-30 sites over three years with an estimated eligible cohort of at least 14,500 patients.

4. Assessment and management of risk

Using the MHRA guidelines this trial has been categorised as: Type A = No higher than the risk of standard medical care. Volatile anaesthetics and propofol are commonly used, standard of care, methods of anaesthesia. In this trial, the IMP will be used within the licensed indication and as per the Summary of Product Characteristics (SmPC).

The side effects for volatile anaesthetics are listed in the SmPC.

Patients that are pregnant, with a known allergy to propofol or with known malignant hyperthermia will be excluded from the trial.

5. Trial objectives and design

5.1.Objective

This single-blind randomised controlled trial is designed to assess the feasibility of the COPIA trial, in terms of recruitment and adherence to the randomised treatment allocation.

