5.6. Primary objectives

Feasibility of the study protocol:

1. Feasibility of meeting recruitment targets. The aim will be to recruit 50 patients across two tertiary cardiac surgery centres within approximately 10 months.

EudraCT Number: 2019-000171-16

2. Identification of potential recruitment barriers with current protocol.

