9.1. Power calculations and sample size determination

50 patients are to be recruited from two centres allocated in a ratio of 1:1. As this is a feasibility trial, power calculations are not appropriate.

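### The 50-patient recruitment target, met exactly, projects to 1,800–2,700 patients at 20–30 sites over three years, short of the 2,900 that Section 3.3 says it would support

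*Protocol*

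**What the plan says.** Section 5.6 gives the first primary objective as meeting the recruitment target: "The aim will be to recruit 50 patients across two tertiary cardiac surgery centres within approximately 10 months". The Synopsis, under the proposed end date, has the same period: "Trial enrolment is projected to complete approximately 10 months after the start of the recruitment period". Section 9.1 repeats the size and number of centres: "50 patients are to be recruited from two centres allocated in a ratio of 1:1". No other numerical recruitment target appears.

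Section 3.3 then says what success would mean for the main trial. Its condition is "If the anticipated recruitment, follow-up and retention rates are demonstrated over a 10 month recruitment period", and its conclusion is that "this would demonstrate the feasibility of a proposed 2900 patient multicentre randomised controlled trial, recruiting at 20-30 sites over three years". The eligible cohort is put at 14,500 or more. The section attaches no number to the anticipated recruitment rate and does not explain how the two-centre result scales to the main trial.

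Section 9.3 makes the rate of recruitment over time, together with adherence to the protocol, the primary outcome measure.

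**The concern.** Recruitment is a primary outcome here, and Section 3.3 is the only place that says what a successful result implies for the main trial. The target in Section 5.6 and the main-trial dimensions in Section 3.3 can be put on one scale, patients per site per month. On that scale they do not agree: a feasibility trial that exactly meets its target shows a rate that does not fill the main trial anywhere in the stated range of sites.

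What is at stake is the planning of the main trial. A funder or steering committee that relied on the sentence could approve too few sites or too short a recruitment period. The conduct, safety monitoring and analysis of the feasibility trial are not affected.

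**Working it through.** **Inputs, all from the protocol.** Target: 50 patients, 2 centres, about 10 months (Section 5.6; also the Synopsis and Section 9.1). Main trial: 2,900 patients, 20–30 sites, three years = 36 months, eligible cohort at least 14,500 (Section 3.3).

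**Can 2,900 be reproduced?** The protocol gives no derivation. The only simple link within Section 3.3 is 2,900 / 14,500 = 20% uptake. That is consistent with 2,900, but it is not tied to the 50-patient target.

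**Rate implied by the target.** 50 / (2 × 10) = 2.5 patients per site-month.

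**Projection, all sites open from day one.** N = 2.5 × sites × 36; required rate = 2,900 / (sites × 36).

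| Sites | N at 2.5 per site-month | Shortfall against 2,900 | Required rate | Equivalent in 10 months at two centres | Time to 50 at required rate |
|---|---|---|---|---|---|
| 20 | 1,800 | 1,100 (38%) | 4.03 | 81 patients | 6.2 months |
| 25 | 2,250 | 650 (22%) | 3.22 | 65 patients | 7.8 months |
| 30 | 2,700 | 200 (7%) | 2.69 | 54 patients | 9.3 months |

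**What 2.5 per site-month would need.** Over 36 months: 2,900 / (2.5 × 36) = 32.2, so 33 sites. At 30 sites: 2,900 / (2.5 × 30) = 38.7 months. At 20 sites: 2,900 / (2.5 × 20) = 58 months.

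**Sensitivity to the word approximately.** If 50 patients take 9 months, the projection is 2,000 at 20 sites and 3,000 at 30. If they take 11 months, it is about 1,636 and 2,455.

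**Sensitivity to site opening (assumption: linear over 12 months).** Each site loses 6 months on average, leaving 30.
- Yield: 2.5 × 20 × 30 = 1,500 to 2.5 × 30 × 30 = 2,250.
- Required rate: 2,900 / (30 × 30) = 3.22 at 30 sites; 2,900 / (20 × 30) = 4.83 at 20.
- At 2.5 per site-month: 2,900 / (2.5 × 30) = 38.7, so 39 sites for 36 months; or, at 30 sites, 38.7 + 6 = 44.7, about 45 months.

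**Sampling error.** The exact 95% Poisson interval for a count of 50 is 37.1 to 65.9. Divided by 20 site-months, this is 1.86 to 3.30 per site-month. Over 36 months with all sites open it projects to:
- 20 sites: 1,336 to 2,373, which excludes 2,900.
- 25 sites (× 25 × 36 = × 900): about 1,670 to 2,966, which only just includes 2,900.
- 30 sites: 2,004 to 3,560, which includes 2,900.

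**The case against.** The strongest reply has four parts.

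*Section 3.3 states no rate.* The anticipated recruitment rate could be an uptake proportion, since 2,900 is exactly 20% of the 14,500 eligible. Reading it as 2.5 per site-month is therefore an inference. That is fair, and the projection should be labelled as resting on it. It does not repair the sentence, because the protocol sets no 20% target and does not link uptake to the 50 patients.

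*The gap at 30 sites is small.* This stands. It is 200 patients, well within sampling error, and a finish at 9.3 months would remove it. But 30 is the most favourable end of the stated range, and at 20 sites even a nine-month finish gives only 2,000.

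*Main-trial sites may recruit differently from these two centres.* They may, in either direction. The protocol offers no other rate, so a higher one would have to be written down.

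*This is a forward-looking statement in a feasibility protocol.* It is true that "As this is a feasibility trial, power calculations are not appropriate", and Section 9.3 says the findings will chiefly help to refine the full trial's design. The observed rate can therefore still reset the site number or duration. This limits the severity, but the projection still does not follow from the target.

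Two stronger readings are tempting and are not supported. A reader might infer that Section 3.3 sets a go/no-go rule on recruitment. It does not: the protocol contains no formal progression rule, and the sentence also depends on follow-up and retention. A reader might also infer from the procedures table in Section 8.1, which marks rate of recruitment in the pre-admission column, that consents rather than randomisations will be counted, inflating the rate. A column in a visit schedule shows when information is gathered; it does not define the numerator. Section 9.1 mentions recruitment and allocation together, and the exact definition may lie in an analysis plan that is not at hand.

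**Conclusion.** The point holds at moderate severity. On the protocol's own figures, meeting the Section 5.6 target exactly gives 2.5 patients per site-month. That projects to 1,800, 2,250 or 2,700 patients at 20, 25 or 30 sites over 36 months, which is 38%, 22% or 7% below 2,900. No point in the stated range reaches 2,900. The gap is minor at 30 sites and material at 20 to 25.

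The conclusion assumes that main-trial sites recruit at the mean rate targeted for the two feasibility centres, that 10 months is taken as stated, and that all sites open on day one. The last is the most favourable case: staggered opening widens the gap.

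The calculation does not show that a 2,900-patient trial is infeasible. A rate modestly above target would fill it at 30 sites, and 50 recruits are too few to rule that out. Nor is the 50-patient target itself an error. What fails is the statement in Section 3.3 that reaching the anticipated rates would establish feasibility across 20 to 30 sites in three years.

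**What to change.** Reword Section 3.3 so that its figures agree, in one of two ways.

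1. **State the required rate.** Give the per-site monthly rate the main trial needs, and say that the observed rate, with its interval, will be judged against it. With all sites open at once this is 2.69 at 30 sites, 3.22 at 25 and 4.03 at 20. If sites open linearly over 12 months (an assumption), it is about 3.22 at 30 sites and 4.83 at 20.
2. **Restate the main trial to match 2.5 per site-month.** With all sites open at once this means at least 33 sites for 36 months, or about 39 months at 30 sites. With 12-month staggered opening it means about 39 sites for 36 months, or about 45 months at 30 sites.

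Either way, say which site-opening assumption is used, since figures based on day-one opening fall short if opening is staggered. If a higher main-trial rate or a 20% uptake is what was meant, state it and link it to what the feasibility trial will measure.

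The 50-patient target in Section 5.6 can stay, and no extra patients or data are needed. The change is to wording only. Its cost is that the stated projection becomes less favourable.

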5.2. Hypothesis

Our overarching hypothesis is that the use of volatile anaesthetics, as the only maintenance for general anaesthesia, without propofol, will reduce postoperative LCOS and myocardial injury in higher risk adult patients undergoing elective CABG or CABG plus valve surgery, when compared to propofol maintenance of anaesthesia.

5.2.1.Definition of Volatile Anaesthetics

Volatile anaesthetic agents are halogenated ethers. Isoflurane (1-chloro-2,2,2-trifluoroethyl difluoromethyl ether) is commonly used in cardiac anaesthesia in the UK. However, sevoflurane (fluoromethyl-2,2,2-trifluoro-1-ethyl ether) or desflurane (1,2,2,2-tetrafluoroethyl difluoromethyl ether) are also in use. Volatile anaesthetics are commonly administered via inhalation by vaporisers together with oxygen and air through the endotracheal tube. In the lungs they diffuse through the alveolar membrane into the blood stream, which is dependent on many variables such as inhaled concentration, alveolar ventilation, blood/gas partition coefficient and pulmonary blood flow. They are used for maintenance of anaesthesia and maintenance dose of the volatile anaesthetic agent will be titrated to doses deemed necessary in order to provide sufficient depth of anaesthesia according to clinical signs of depth of anaesthesia and the blood pressure.

EudraCT Number: 2019-000171-16

5.3. Inclusion criteria

- 1. Patients (male and female) aged 18 years and above
- 2. Written informed consent to participate
- 3. Patients undergoing Coronary Artery Bypass Graft (CABG) surgery on Cardiopulmonary bypass (CPB) with or without valve surgery
- 4. Additive European System for Cardiac Operative Risk Evaluation (EuroSCORE) of 5 or higher (higher scores indicating a greater risk of death; 0 indicates minimum risk and ≥6 indicates high risk)

5.4. Exclusion criteria

- 1. Pregnant or lactating women
- 2. Allergy to propofol
- 3. Previous diagnosis or suspected malignant hyperthermia
- 4. Patients with a known sensitivity to any of the IMPs or other halogenated anaesthetics
- 5. Concomitant therapy with Glibenclamide, Allopurinol, Theophylline or Nicorandil (medications that may interfere with remote ischemic preconditioning)
- 6. Inclusion in another clinical trial of an investigational medicinal product within the last 3 months.

5.5. Statement on co-enrolment

Patients may be entered into registries or observational studies while also participating in COPIA. Patients may not be entered into other IMP trials, research where coenrolment would be burdensome for the patient, or into any other research where the trial treatment will interfere with the COPIA intervention and primary outcome.

5.6. Primary objectives

Feasibility of the study protocol:

1. Feasibility of meeting recruitment targets. The aim will be to recruit 50 patients across two tertiary cardiac surgery centres within approximately 10 months.

EudraCT Number: 2019-000171-16

2. Identification of potential recruitment barriers with current protocol.

5.7. Secondary objectives

- Feasibility of collecting event data in more than 95% of enrolled patients at the 30 day follow-up.
- Assessment of effectiveness of patient identification and screening processes.
- Identification and analysis of any reasons for failure to recruit patients.
- Assessment of trial processes, including the choice of outcome measures and impact on staff.
- Assessment on the feasibility of collecting the following, planned to be endpoints in the full trial:
 - Low Cardiac Output Syndrome
 - Myocardial injury, assessed by ischaemic serum markers: hsTnT, MyC, preoperatively, at 6 hrs after arrival in CCU and on the 1st and 2nd postoperative mornings, area under the curve and peak postoperative levels
 - MACCE (stroke, non-fatal myocardial infarction, death from any cause) at 30 days
 - Cardiac related mortality at 30 days
 - Postoperative in hospital atrial fibrillation requiring treatment
 - Acute kidney injury (according to KDIGO)
 - In-hospital postoperative delirium (assessed by the confusion assessment method) [17]
 - Respiratory complications needing prolonged ventilation (>24 hours)
 - Length of stay in the critical care unit (CCU)
 - Length of hospital stay
 - WHO Disability Assessment Schedule (WHODAS) at 30 days [18]
 - Quality of Life Questionnaire, Eurogol EQ-5D-5L at baseline and 30 days
 - Days alive and at home until 30 days after surgery

